9. STUDY SUBJECTS AND DEMOGRAPHICS

9.1 Disposition of Subjects and Withdrawals

The numbers and percentage of subjects screened, randomized, completing the study, and withdrawing from the study, along with reasons for withdrawal, will be tabulated overall and by treatment group. The number and percentage of subjects in each analysis population will be reported. Additionally, the number and percentage of subjects that have an investigator-directed dose reduction from two tablets per day to one tablet per day will be summarized. The disposition and withdrawal summaries will be based on all subjects who have data entered into the database.

9.2 Protocol Violations and Deviations

Protocol deviations will be checked on complete data for all subjects. Protocol deviations will be summarized by type, status as major vs minor, and by treatment group for the Safety population.

Individual subjects with protocol deviations or violations will be listed.

9.3 Demographics and Other Baseline Characteristics

Descriptive summaries of the demographic and other baseline characteristics will be completed for all enrolled subjects in the study population by treatment groups, unless otherwise specified.

Descriptive summaries of demographic and other baseline conditions will include:

- Demographics (age, gender, race/ethnicity, height, weight, BMI, family status, education and employment status)
- Tobacco/nicotine, alcohol, and THC/cannabis use history
- ACR Criteria

Medical History will be coded using the Medical Dictionary for Regulatory Activities (MedDRA) version 22.1 and summarized by SOC and Preferred Term using frequency counts by treatment group. Physical examination data, as well as findings from dedicated oral cavity examinations, will be presented in listings.

10. EFFICACY ANALYSES

10.1 Primary Efficacy Analysis

10.1.1 Estimand

The primary ITT analysis will provide an estimate of the following causal estimand: the difference in the weekly mean change from Baseline of the daily subject self-reported 24-hour recall average pain severity rating using an 11-point (0-10) NRS evaluated at the Week 14 endpoint in all randomized subjects attributable to the initially randomized treatment assignment, under the assumption that those withdrawing due to AEs and lack of efficacy revert to the baseline pain levels (on average).

10.1.2 Primary Analysis

An adaptive group sequential design will be performed by an independent third party statistical group [REDACTED] to cover an early efficacy stop, sample size adjustment, or futility stop; the final CSR analyses in all cases will be performed by [REDACTED] (the primary biostatistics vendor). To assure independence of the stage wise test statistics, the first stage population is defined as the first half of the subjects randomized, planned as 236. The second stage population is defined as all subjects randomized after the interim cut-off.

The interim analysis will be executed once all subjects in the Interim Population either drop out or reach Week 14.

If the study is stopped early for efficacy, subjects who were randomized after the interim cut off will not be included in the efficacy analyses. For early stop, safety analyses will be reported both on all subjects exposed (the Safety Population) and all subjects exposed in the Interim Population (Early Stop Safety Population).

Data of different stages will be combined using the inverse normal method to test the null hypotheses that there is no difference in the change from weekly average of daily pain between TNX-102 SL and placebo treatment groups at Week 14: ([Cui 1999](#)):

$$Z_1 = \Phi^{-1}(1 - p_1)$$
$$\text{and } Z_2 = w_1 Z_1 + w_2 \Phi^{-1}(1 - p_2)$$

Where:

Z_1 = the Z statistic for the first stage

Z_2 = the combination test statistic at the end of the second stage

w_i = the weighting applied for each associated Z statistic

p_1 = the first stage p-value

p_2 = the second stage p-value based on second stage participants

For maximum statistical efficiency, the weights are defined prospectively according to the

square-root of the planned proportion of participants in the two stages, relative to the preplanned total enrollment of 470 participants, as $w_i = \sqrt{0.5}$. The calculation of these weights is fixed and will not be changed due to unblinded data and is hence in line with the draft guidance on adaptive design clinical trials ([CDER, CBER, February 2010](#)). In order to control the type-I error, adaptive changes of the stage wise sample sizes will not lead to changes of the weights ([Lehmacher & Wassmer 1999](#)).

The mean change from baseline in the weekly average of daily pain scores from baseline to each week in the TNX-102 SL and placebo arms will be analyzed using a restricted maximum likelihood (REML) based repeated measures approach with data imputed using multiple imputation (see [Section 8.1.3](#)). Week 14 will serve as the primary time point of interest. Models will be run on each of the twenty imputation sets individually and will include the fixed, categorical effects of treatment, site, study week, and treatment by study week interaction, as well as the fixed covariates of baseline value and baseline value score-by-study week interaction. An unstructured covariance structure will be used to model the within-subject errors. If this analysis fails to converge, the following structures will be tested in this order: first order ante dependence, heterogeneous first order autoregressive, heterogeneous compound symmetry and compound symmetry with the first to give convergence used. The Kenward-Roger approximation will be used to estimate the denominator degrees of freedom. LS means and differences across the twenty MI reps will be combined using SAS procedure MIANALYZE ([Rubin, 1976](#)). Significance testing will be based on least-squares means and two-sided 95% confidence intervals will be presented. [REDACTED]

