2. OVERVIEW

This SAP describes the planned analysis and reporting for Protocol TNX-CY-F304 (A Phase 3, Double-Blind, Randomized, Multicenter, Placebo-Controlled Study to Evaluate the Efficacy and Safety of TNX-102 SL Taken Daily at Bedtime in Patients with Fibromyalgia).

The structure and content of this SAP provides sufficient detail to meet the requirements identified by the FDA, European Medicines Agency (EMA), and International Council for Harmonisation (ICH) of Technical Requirements for Registration of Pharmaceuticals for Human Use: Guidance on Statistical Principles in Clinical Trials. All work planned and reported for this SAP will follow internationally accepted guidelines for statistical practice, as published by the American Statistical Association and the Royal Statistical Society.

The planned analyses identified in this SAP may be included in clinical study reports (CSRs), regulatory submissions, or future manuscripts. Also, post-hoc exploratory analyses not necessarily identified in this SAP may be performed to further examine study data. Any post-hoc, or unplanned exploratory analysis performed will be clearly identified as such in the final CSR.

[REDACTED]

- | [REDACTED]
- | [REDACTED]
- | [REDACTED]
- | [REDACTED]
- | [REDACTED]
- | [REDACTED]

The reader of this SAP is encouraged to also read the clinical protocol, and other identified documents, for details on the planned conduct of this study. Operational aspects relating to collection and timing of planned clinical assessments are not repeated in this SAP unless they are relevant to the planned analysis.

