7. ANALYSIS POPULATIONS

The following analysis populations are planned for this study:

- **Safety Population (SAFETY):** all subjects who took investigational product. Subjects that were issued study drug, but do not return all of it will be included in the safety population. All safety analyses and demographic/baseline characterization will be performed using this population, analyzed as treated.
- **Intention-To-Treat Population (ITT):** all subjects who were randomized. This is the primary population for efficacy analyses, and subjects will be analyzed based on their randomized treatment.
- **Interim Population:** approximately the first 235 subjects randomized; this will be utilized for the interim analysis, if performed. In the case of an early stop, this will serve as the population for efficacy analyses. The cutoff of the population will be the date that the 235th subject is randomized; thus it is possible to have a marginal overrun depending on the number of subjects randomized that day.
- **Early Stop Safety Population:** all subjects that are in the safety population and the interim population. This will serve as a population parallel to the Interim Population for the purpose of evaluating the risk/benefit on the same sample.

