8.1.3 Imputation of Missing Data

For individual daily pain scores, since a mean is used in the calculation of the primary endpoint, it is not necessary to replace values missing on random intermittent days; weeks will have average values as long as a single value for that week is present.

Missing weekly pain scores for participants in the ITT population will be imputed via multiple imputation (MI). When the study medication was discontinued due to lack of efficacy (LOE) or due to an AE, missing values will be imputed drawing from the baseline values, conditioned on the non-missing weekly average post-baseline values, of all participants in the ITT population under the assumption that they are missing not at random (MNAR), with a covariate for site. If the study medication was discontinued for any other reason (including impacts from the COVID-19 pandemic), values will be imputed within treatment group using MI under the assumption that they are missing at random (MAR) with covariates for site and the average pain severity score recorded at each time point. The MAR approach will also be applied for sporadic missing values (prior to discontinuation). The MI process will use twenty repeats in the analysis datasets generated; seeds are given in [Appendix D](#). For the purposes of the MI, all sites with less than 10 subjects will be pooled into a single large site; this will be done for both the interim and post interim samples.

The steps will be as follows:

1. Intermittent missing weekly average scores will first be imputed using the Markov Chain Monte Carlo (MCMC) method implemented with the SAS MI procedure, which is appropriate for non-monotonic missing data.
2. For subjects that do not discontinue for LOE or AEs, a MAR imputation will be applied: the monotone missing values will then be multiply imputed with the SAS MI procedure using the monotone regression method. Baseline average and the weekly scores will be included as covariates as well as site; imputation will be done within treatment group.

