3. For subjects that discontinue for LOE or AEs, an iterative process will be applied moving through each week. The complete MAR dataset from step 2 above will be used and augmented with subjects missing for the week being imputed at that stage. The non-missing values for the week in question will temporarily be set to the subjects corresponding baseline value, so the data from LOE and AE subjects are imputed for that week drawing from the baseline distribution. This will proceed from Week 1 to Week 14 with the imputed complete dataset for a week serving as the basis for the subsequent week. Covariates at each stage will include the values for the prior weeks (observed, MAR imputed in steps 1& 2, or imputed previously in this step) and site.

The above process will be done independently for the subjects included in the interim analysis and those not in the interim.

Daily sleep diary data will be handled in an identical manner to the pain scores.

Continuous outcomes included in the list of key secondary outcomes that are collected in-clinic will be handled as above, minus the step of creating weekly averages of daily values and with steps being done by visit instead of week.

Subjects with missing PGIC at a given visit will be considered non-responders at that visit for the purposes of treatment comparisons and efficacy claims; additional tabulations will summarize the number and percentage in each category out of non-missing values as well as a count of the missing values.

No missing safety data will be imputed.

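### After an early efficacy stop the SAP leaves every subject randomised after the interim cut-off out of efficacy, and no readable text plans a supplementary estimate that includes them

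*SAP*

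**What the plan says.** SAP 10.1.2 states that after an early efficacy stop "subjects who were randomized after the interim cut off will not be included in the efficacy analyses". SAP 7 agrees, saying of the Interim Population: "In the case of an early stop, this will serve as the population for efficacy analyses". The restriction comes with a reason: SAP 7 defines an Early Stop Safety Population on the same subjects "for the purpose of evaluating the risk/benefit on the same sample". The only overrun rule in readable text covers subjects randomised on the cut-off day itself.

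Safety is treated differently. SAP 10.1.2 adds that "safety analyses will be reported both on all subjects exposed (the Safety Population) and all subjects exposed in the Interim Population".

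Elsewhere the scope is wider. SAP 7 defines ITT as everyone randomised and makes it the primary efficacy population, and the estimand in SAP 10.1.1 also covers all randomised subjects.

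None of the four sensitivity analyses (SAP 10.1.3), the secondary analyses (10.2) or the exploratory analyses (10.3) brings later subjects back after a stop. SAP 2 leaves one route: "Any post-hoc, or unplanned exploratory analysis performed will be clearly identified as such in the final CSR".

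**The concern.** An estimate taken only from the cohort that crossed a stopping boundary tends to overstate the effect, because the cohort is reported on condition that its result was large. Subjects randomised after the cut-off are not selected in that way. SAP 5.1 puts the interim about 18 weeks after the cut-off: 14 weeks of follow-up and 4 of cleaning. If enrolment is not paused, some later subjects will therefore have finished Week 14, with data recorded blind, when the stop is announced.

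Readers will ask what those subjects showed. Under the readable plan the answer could only be a post-hoc analysis, which carries less weight than one fixed in advance. At stake are some precision, some selection bias and the credibility of the supportive estimate. The stopping decision is not at stake.

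**Working it through.** **The plan's own figures.** Half of 470 is 235, against 235 in SAP 7 and 236 in SAP 5.1 and 10.1.2, so they agree to within one subject. The timing also reproduces: 14 + 4 = 18 weeks. The 470 cannot be checked, because its assumptions are redacted.

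**Inputs.** First stage 236 (SAP 10.1.2). Readout 18 weeks = 126 days after the cut-off (SAP 5.1). Week 14 visit allowed up to Day 106 (SAP 8.2.1). Study period 14 months (Protocol Synopsis). Participation 15 to 19 weeks per subject (Protocol 7.3).

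**Assumptions.** The documents give no accrual rate and do not say whether enrolment pauses. I assume that enrolment continues, that accrual is uniform, and that the true effect is the same in both groups.

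**Later subjects available.**
- 14 months is about 60.9 weeks. Less 15 to 19 weeks, that leaves 45.9 to 41.9 weeks of accrual.
- Rate: 470/45.9 = 10.2 to 470/41.9 = 11.2 per week.
- Past Day 106 at the readout: (126 − 106)/7 = 2.86 weeks × rate = 29 to 32 subjects. All interim subjects are past Day 106 by then.
- At half the pace: about 15 to 16 subjects.
- SAP 4 gives up to 21 weeks per subject. That makes 470/39.9 = 11.8 per week and about 34 subjects, which changes little.

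**Interval width without them, relative to with them:** √((236 + m)/236).
- m = 29: √(265/236) = 1.060. m = 32: √(268/236) = 1.066.
- m = 15 to 16: 1.031 to 1.033.

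**Expected overstatement given a stop (illustration only).** The boundary and power are redacted. Let d = k(1.96 + z_power)√0.5 be the expected stage-one Z, with k = true effect/design effect. Let b be the boundary. Then R = E[Z₁ | Z₁ > b]/d on the interim set, and (236R + m)/(236 + m) once m later subjects are added.
- b = 2.797, 90% power, k = 1: d = 3.242 × 0.7071 = 2.29, P(stop) = 0.31, R = 1.499. With m = 29: (353.8 + 29)/265 = 1.445. With m = 32: (353.8 + 32)/268 = 1.440.
- Same b and power, k = 1.5: d = 3.44, P(stop) = 0.74, R = 1.128. With m = 29 to 32: 1.114 to 1.113.
- Over b = 2.178 to 3.291 and 80 to 95% power at k = 1, R runs from 1.227 to 1.898. With m = 32 the low end becomes (289.6 + 32)/268 = 1.20. With m = 29 the high end becomes (447.9 + 29)/265 = 1.80. P(stop) runs from 0.64 to 0.10.

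**Why the planned imputation needs an exception.** SAP 8.1.3 says: "The above process will be done independently for the subjects included in the interim analysis and those not in the interim". It also says: "Baseline average and the weekly scores will be included as covariates as well as site; imputation will be done within treatment group". At Week 14 that means baseline plus 13 earlier weeks, at least 14 predictors, plus site. The 29 to 32 later subjects give about 15 to 16 per arm before any dropout, too few to impute alone. Spread over 35 to 45 sites they average 29/45 = 0.6 to 32/35 = 0.9 per site. The rule that "all sites with less than 10 subjects will be pooled into a single large site" would then merge nearly all of them into one site.

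**The case against.** **This is a design choice.** Two SAP sections state the restriction, SAP 10.1.2 ties the staging to independence of the stage-wise statistics, and SAP 7 gives the same-sample purpose. That stands for the confirmatory analysis. A reader might infer that the interim test is invalid, that type I error is inflated, or that ITT has been breached by oversight. The documents support none of these: first-stage subjects are fixed by order of randomisation, and the exception is explicit. A design reason for the test is not a reason to have no planned supportive estimate.

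**The rule may be elsewhere.** Text in SAP 5.1, 8.1.1.1 and 10.1.2 is redacted, and SAP 14 lists a separate interim SAP and an IDMC charter. This stands as a limit. A reader might infer that the plan as a whole lacks such an estimate, but only its absence from readable text can be stated.

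**The gain is small.** This stands. Adding 29 to 32 subjects dilutes the selection bias without removing it. A bias-adjusted estimate would address selection more directly; the readable text plans none, and it would complement this one. Averaged over all trials, ignoring futility stops and sample-size increase, the overstatement in the first illustration is only about 1.08 times: 0.307 × 1.499 + 0.693 × (0.779 + 1)/2, where 0.779 is the stage-one ratio when the trial continues. With the later subjects it is about 1.06.

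**Larger counts are tempting.** A reader might count everyone past Day 98 (4 weeks × 10.2 to 11.2 = 41 to 45) or everyone randomised by the readout (18 weeks × rate = 184 to 201). The Day 98 count includes subjects whose visit window is still open. The second includes subjects still on treatment, and Protocol 13.6 discontinues the study and unblinds at a stop, so complete blinded data from them cannot be assumed.

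**Pooled imputation changes two things at once.** This is fair, and the fix answers it with an interim-only estimate under the same imputation.

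**Conclusion.** The point holds as a cheap improvement. Followed as written, the readable plan gives a somewhat less precise and more selected effect estimate after an early efficacy stop than the data would allow, and any supportive estimate would have to be labelled post hoc.

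The size is modest: an interval about 6 to 7% wider, or about 3% at half the accrual pace. In the illustration, overstatement given a stop falls from about 1.50 to about 1.44 times when the true effect equals the design effect, and from 1.13 to 1.11 at 1.5 times the design effect. These figures rest on continued, uniform enrolment, a common true effect, and an assumed boundary and power. The point has no effect unless the interim, which SAP 5.1 calls optional, is run and stops for efficacy.

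Protocol 13.6, SAP 4.3 and SAP 5.1 to 5.2 differ on follow-up and blinding after a stop. They need reconciling, but that is a separate point and adds no weight here.

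**What to change.** Keep the stopping decision, alpha and key secondary sequence on the Interim Population. If the interim SAP, the IDMC charter or redacted text already covers this, a cross-reference is enough. Otherwise add to SAP 10.1.2, with a matching line in SAP 7:

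*After an early efficacy stop, a supplementary estimate with 95% CI, not a further test, will be given for the primary and key secondary endpoints. It will include all subjects, interim and later, whose Week 14 window (Day 106) closed before the stop was announced or treatment revealed, whichever came first. Only data recorded before that date will be used, with the planned models. For this estimate only, imputation and site pooling under Section 8.1.3 will be run on both groups together. The interim-only estimate under the same pooled imputation will be shown beside it.*

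One date rule for every endpoint keeps the set of subjects the same. It also prevents a missing PGIC from being scored as non-response (SAP 8.2.3) while the visit is still allowed. The interim-only companion separates the effect of adding subjects from the change of imputation. It is needed for the six continuous endpoints (pain and five secondaries), because PGIC is not multiply imputed.

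Cost: wording in two SAP sections and some extra programming, with no added subjects or visits. The downside for the sponsor is that the supplementary effect may look less favourable than the interim one.

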10.1.3 Sensitivity Analyses

Four sensitivity analyses will be performed:

For the first, pain scores will be censored on the day(s) on which an opioid is utilized. If the subject utilizes an opioid for any indication, then the pain score on each impacted day will be replaced by the score obtained on the day immediately prior to the first day of opioid use (and until the opioid is no longer used). This will be done prior to the weekly averaging, and all other calculations will be performed as described in the primary. This will investigate whether use of concomitant opioids influences the interpretation of study results.

For the second, subjects that discontinue due to “withdrawal of consent” or “investigator decision” will be grouped with the LOE and AE dropouts when performing the multiple imputation procedure. This analysis will investigate whether the categorization of these reasons for dropout influences the interpretation of study results.

For the third, ALL subjects that discontinue will be grouped with the LOE and AE dropouts when performing the multiple imputation procedure. This analysis will sample from the baseline distribution of all dropouts and will investigate whether treating dropouts as treatment failures (on average) influences the interpretation of study results.

Finally, a tipping point analysis will be performed on the values for the primary analysis. A shift parameter will be applied to the active treatment arm starting at .25 and increasing in increments of .25 through either 5 or when the outcome is no longer significant. This will only be performed if the primary analysis is significant. This will test the overall robustness of the

primary analysis.

